9.5.2.8.3 Safety Urinalysis

The following parameters will be analyzed in fresh midstream urine.

pH	Ketones
Specific gravity	Bilirubin
Protein	Blood
Glucose	

Microscopic examination will be conducted if blood is detected during urinalysis. The microscopic examination will comprise of RBC, WBC, casts, and bacteria.

9.5.2.8.4 Urine Pregnancy Test

In all female participants a urine beta-HCG test will be performed on fresh midstream urine at screening and on day 180.

9.5.2.8.5 Serum Pregnancy Test

A 7.5 mL sample of blood will be drawn into a Serum Monovette and the following parameter will be assessed at the time points described in Table 1:

β-HCG

9.5.2.8.6 Cardiac biomarker

A 4.9 mL sample of blood will be drawn into serum separator tube (**Z-Gel**) at the time points described in Table 1. The following parameters will be assessed.

Troponin T

9.5.2.8.7 Serology

During the screening period only, two blood samples of approximately 7.5 mL will be drawn into a serum separator tube (**Z- Gel**) to test for the presence of HIV, Hepatitis B and C:

HIV antibody (HIV I and HIV II)	HCV antibody screen
HBsAg	

9.5.2.8.8 Drug and Alcohol Screen

An alcohol breath test and urine screen for drugs of abuse will be performed at the time points described in Table 1. Additional drug and alcohol screens may be performed at the investigator's discretion.

Urine samples are to be tested for the following:

Methadone (MTD)	Barbiturates
Benzodiazepines	Tricyclic Antidepressants (TCA)
Cocaine	Morphine
Amphetamine/Methamphetamine (MET)	Tetrahydrocannabinol (THC)
Ecstasy	

9.5.2.8.9 Reactogenicity

To assess reactogenicity after each immunization body temperature and reaction are recorded for at least 14 days after vaccination or until any symptoms resolved if longer. According to the defined time frame of ± 2 days for the ambulatory visit on day 42 recording might be shortened to day 40. During confinement at the study ward temperature and solicited injection site and systemic reactions will be assessed and recorded by a designated member of the study team. After dismissal subjects are asked to maintain a diary to record daily temperature and solicited (expected) injection site and systemic reactions for 14 days after each dosing. Subjects will be asked to maintain a second diary for another 14 days to record medicinal events. As described above, the second diary after the second immunization should be maintained at least until day 40. Subjects will be trained on the thermometer and diary use.

The following items will be recorded:

- Daily temperature (incl. the method by which it was taken)
- Daily measurement of intensity grade of all other solicited (expected) injection site and systemic reactions
- Action taken for each recorded event (none, medication taken, physician consulted, hospitalization)

9.5.2.8.10 Local Reaction Assessments

Local reactions, resulting from the IMP, will be graded using a local reaction assessment scale

Grade Description:

- 0 = None
- 1 = Mild macular or papular eruption, erythema, or induration that is asymptomatic or mildly symptomatic.
- 2 = Moderate macular or papular eruption, erythema or induration with pruritus, mild blistering or other associated moderate symptoms.
- 3 = Severe ulceration, superinfection, severe blistering, or phlebitis.
- 4 = Potentially life-threatening necrosis of the skin.

9.5.2.8.11 Adverse and Serious Adverse Events Assessments

Subjects will be questioned in a general way to ascertain if AEs have occurred (e.g. "Have you had any health problems since the last time you came to the clinic/since you were last questioned?"). This open, standardized questioning should be done discretely in order to prevent subjects from influencing each other. Spontaneous reports of AEs will also be recorded as well as AEs that are observed by the investigator or a staff member.

All AEs will be reviewed, confirmed, and classified by a qualified, designated physician.

9.5.3 Pharmacodynamic Measurements

Detailed information about blood sampling and processing of the samples are defined in the safety/lab manuals.

9.5.3.1 Immunogenicity Assays

The information on the blood volume drawn for immunogenicity assays given below refer to maximum amounts. Details on the exact blood volume are specified in the laboratory manual.

9.5.3.1.1 Enzyme-Linked Immunosorbent Assay (ELISA)

To identify binding MVA-MERS antibody responses induced by the candidate vaccine ELISA assays will be performed on serum samples (7.5 mL serum tube) drawn at the time points described in Table 1. The analysis will be performed at the Institute for Virology in Marburg, Germany according to the process defined in the Safety/ Laboratory Manual. Seroconversion will be defined as at least a two-fold rise in titers, or becoming seropositive in originally seronegative subjects.

9.5.3.1.2 Neutralization Assay

Neutralization antibody responses against MVA will be measured on the same serum sample used for ELISA (7,5 mL serum tube) obtained at the time points described in Table 1 using a luciferase based

assay in HeLa or DF-1 cells. The analysis will be performed at the Institute for Virology in Marburg, Germany according to the process defined in the laboratory manual.

9.5.3.1.3 T cell IFN- γ ELISPOT

The magnitude, kinetics and epitope targets of MVA-MERS T-cell responses will be assessed by IFN- γ ELISpot assay. The assay will be performed on cryopreserved PBMC samples (from 4 x 9 mL EDTA tubes) obtained at the time points described in Table 1. The analysis will be performed in the Virus-Immunology Research Laboratory, Heinrich-Pette-Institute, Hamburg, Germany according to the process defined in the Laboratory Manual.

Blood samples (36 mL) for T cell immunogenicity analysis (2 x 9 mL for ELISpot and 2 x 9 mL for ICS) will be drawn by direct venipuncture into four EDTA tubes, capped and mixed by inversion (x3). The actual time that the sample was obtained will be recorded on the source documents. After applying a tourniquet, venous blood will be taken with a disposable needle.

The labels will contain the following information:

Study Number

Study Day and Time point

Subject Identifier

9.5.3.1.4 Sample preservation for Intracellular Cytokine Staining for MERS-S-specific CD4 and CD8 T cell responses

The magnitude and kinetics of MERS-S-specific CD4 and CD8 T-cell responses will be determined from cryopreserved PBMC at the time points described in Table 1 using flow cytometry (from 2 x 9 mL EDTA tubes as above). The analysis will be performed by [name] and [name] [name]'s group at the UKE, hosted in the Virus-Immunology Research Laboratory, Heinrich-Pette-Institute, Hamburg, Germany according to the process defined in the Laboratory Manual.

9.5.3.1.5 Sample preservation for RNA analysis

In the exploratory translational research program gene expression analysis from whole blood (2.5 mL Paxgene tube) will be performed at baseline and early time points post-vaccination to investigate early innate immunity gene signatures induced by the vaccine candidate and their impact on adaptive B and T cell immunity.

9.5.3.1.6 Innate immunity

To evaluate early innate immunity gene expression signatures cryopreserved PBMC at the time points described in Table 1 will be analyzed using flow cytometry (from 2 x 9 mL EDTA tubes). Furthermore, plasma obtained after centrifugation of the EDTA tube will be analyzed via luminex multiplex assays.

9.5.3.1.7 Isolation of antigen-specific B cells

Cryopreserved PBMC will be shipped to [name] at the University of Cologne for the isolation of MERS-S specific B cells using flow-cytometry.

9.5.3.2 Shipment of Immunogenicity Samples

All samples, along with the corresponding documentation, will be transported from the CTC North to the Heinrich-Pette Institute, Leibniz Institute for Experimental Virology (AG [name]), UKE campus, building N 63 for further processing.

After processing frozen serum samples for MVA-MERS antibodies will be shipped from there to the Institute of Virology in Marburg ([name]):

Institute for Virology
Philipps University Marburg
[name], Germany

[contact]
[contact]
[contact]
Email: [contact]

After processing frozen PBMC samples for MVA-MERS B cells will be shipped from there to the laboratory for experimental Immunology ([name]):

Labor für Experimentelle Immunologie
Klinik I für Innere Medizin
Zentrum für Molekulare Medizin
Universität zu Köln
[name]

[contact] Email
Email: [contact]

9.5.3.3 Samples for cellular response and exploratory translational samples

Samples, along with the corresponding documentation, will be transported from the CTC North to:

[name], UKE Emerging Infections
Heinrich Pette Institute, UKE Campus, Building N 63
[name]
20251 Hamburg, Germany

Shipment and storage procedures are defined in the Laboratory Manual.

9.5.3.4 Future Use of Stored Samples

Left over blood samples may be used in the further evaluation of an adverse event or for the subsequent evaluation of additional parameters that are identified as important to the evaluation of an individual subject or to the study, or for further research regarding the immune response to the MVA-MERS vaccine. Any unused part of the blood samples will be securely stored in [name] laboratory for up to 15 years. Parts of the blood samples may pseudonymized be shipped to collaborators for further evaluation.

9.5.3.5 Safety Variables

Assessment of safety is performed for the safety set. Safety data include:

- Adverse events (including changes from baseline in physical examination findings)
- Clinical laboratory results
- Vital signs
- 12-lead ECGs

The safety evaluation will be based upon the review of the individual values (potentially clinically important abnormalities) and descriptive statistics (summary tables, graphics) (see section 9.8).

9.5.3.5.1 Adverse Events

The adverse events will be listed per subject using MedDRA terminology (preferred term and system organ class) and will be reported in tables summarizing the frequency of subjects with adverse events and adverse events by dosage level, by dose level and injection and by body system, the number of adverse events and number of subjects with adverse events by dosage level, by dosage level and injection, and the characteristics of adverse events.

For the hematology, clinical laboratory and the urine analysis deviations from the reference ranges will be summarized in frequency tables.

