Statistical methods:	
Metric data will be summarized using descriptive statistics (number, mean, standard deviation, minimum, median and maximum). Categorical data will be summarized by using frequency tables (frequency and percent). It is not planned to test any hypotheses in a confirmatory sense.

STUDY SCHEDULES

Table 1a

Phase of study	SCR	Confinement			Ambulatory Visits			Confinement			Ambulatory Visits				End of study
Study day	-28- -2	-1	0	1	3	7	14 (±2)	27	28	29	35	42 (±2)	56 (±3)	84 (±3)	180 (±7)
Informed Consent	√														
I/E Criteria	√	√						√							
Medical History/ De-mographics	√														
Update Medical History		√						√							
Physical Examination	√	√ ^a						√ ^a				√ ^a			√
Height and Weight	√														√ ^c
Vital Signs	√	√	√ ^d	√	√	√	√	√	√ ^d	√	√	√	√	√	√
12-lead ECG	√					√	√		√		√	√			
Ambulatory Visit	√				√	√	√				√	√	√	√	√
Confinement		√	√	√ ^e				√	√	√ ^e					
Dosing			√ ⁱ						√ ⁱ						
Injection site & systemic events/ reactions assessment			√ ^d	√	√	√	√		√ ^d	√	√	√			√
Temperature	√		√ ^d	√	√	√	√		√ ^d	√	√	√	√	√	√
Alcohol Breath Test	√	√						√							
Discharge				√						√					
Training/ Dispensing subject diary			√						√						
Review/ Collection of subject diary				√	√	√	√	√		√	√	√	√	√	√
Adverse Events & Concomitant medication			√ ^d	√	√	√	√	√	√ ^d	√	√	√	√	√	√
Laboratory Analysis															
Phase of study	SCR	Confinement			Ambulatory Visits			Confinement			Ambulatory Visits				End of Study
Study day	-28- -2	-1	0	1	3	7	14 (±2)	27	28	29	35	42 (±2)	56 (±3)	84 (±3)	180 (±7)
Troponin T	√					√	√		√		√	√			√
Safety Lab blood (Clinical Chemistry, Hematology)	√	√		√	√	√	√	√		√	√	√			√
Safety Lab Urine	√	√				√	√	√			√	√			√
HIV/HBV/HCV Serology	√														
Urine Drug Screen	√	√						√							
Pregnancy Test	√ ^h	√ ^g						√ ^g							√ ^h
Anti-MVA-MERS Elisa			√			√	√		√		√	√	√	√	√
Neutralization Assay			√			√	√		√		√	√	√	√	√
T-cell response			√			√	√		√ ^f		√	√	√	√	√
RNA blood sample storage			√	√	√	√			√ ^f	√	√				

Innate immunity			√	√	√	√			√	√	√				
PBMC freezing and plasma aliquots			√	√	√	√	√		√ _f	√	√	√	√	√	√

Table 2b**3rd boost vaccination 8-16 months after initial vaccination**

Phase of study	Phone Call	Dosing	Ambulatory Visits				End of study
Study day	≥ - 7	0	1	3	7	14 (±2)	28(±2)
Informed Consent		√ _f					
I/E Criteria		√ _f					
Update Medical History		√ _f					
Physical Examination		√ _{af}					
Weight		√ _{fc}					
Vital Signs		√ _d	√	√	√	√	√
12-lead ECG		√ _f					

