9.3.3.3 Criteria for Termination of the Study (Holding Rules)

Safety holding rules will apply throughout the entire study period. Further injections will be discussed with the Local Safety Board. Should a holding rule be activated, the PI will inform the sponsor. The sponsor has to inform the competent authorities and the ethics committee within 15 days.

If the event(s) occur in the higher-dose cohort, the follow-up phase of the lower dose cohort will continue. The discontinuation of a holding rule should be communicated to all entities in the same manner and timeframe as described above.

The Local Safety Board review will consider:

- The relationship of the AE or SAE to the vaccine
- The relationship of the AE or SAE to the vaccine dose, or other possible causes of the event
- If appropriate, additional screening or laboratory testing for other subjects to identify those who may develop similar symptoms, and alterations to the current informed consent form will be discussed

All injected subjects will be followed for safety until resolution or stabilization (if determined to be chronic sequelae) of their AE. AE grading will be done according to FDA's 2007 voluntary guidance: (14) or according to CTCAE v4 (15). Please refer to Table 3- Table 5 for further details.

The holding rules are as follow:

- Solicited (expected) local adverse events:
 - If more than 25% of injections (minimum 2 individuals) are followed by Grade 3 solicited swelling or pain or Grade 4 redness beginning within 3 days after injection (day of injection and one subsequent day) and persisting at Grade 3 (swelling or pain)/4 (redness) for >48 – 72 hours
- Solicited (expected) systemic adverse events:
 - If more than 25% of injections (minimum 2 individuals) are followed by Grade 3 solicited systemic AE (or Grade ≥ 3 physical observations as defined above and in Section 9.7.11) beginning within 3 days after study injection (day of injection and one subsequent day) and persisting at Grade ≥ 3 for >48 – 72 hours
- Unsolicited (unexpected) adverse events:
 - If more than 25% of subjects (minimum of 2 individuals) develop a Grade ≥ 3 unsolicited AE (including laboratory AE and physical observations) that is considered probably or definitely related to injection and persists at Grade 3 for >48 – 72 hours
- A serious adverse event occurs that may be related to the IMP

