9.4.10.3.2 Screening

At the screening visit the following interventions will be performed:

- Informed Consent
- I/E Criteria
- Medical History/ Demographics
- Physical Examination
- Vital Signs/Temperature
- ECG
- Height and Weight
- Alcohol Breath Test
- Urine Drug Screen
- Urine Pregnancy Test
- HIV/HBV/HVC Serology
- Safety Laboratory (Urine/Blood)
- Troponin T

9.4.10.3.3 Confinement Day -1 to Day 1 and Day 27 to Day 29

During confinement the following interventions will be performed:

- I/E Criteria check
- Update medical history
- Targeted physical examination
- Vital signs / Temperature
- 12-lead ECG (only on day 28)
- Injection Site reaction & systemic events/reaction assessment
- AE/ConMed
- Alcohol Breath Test
- Urine Drug Screen

- Serum Pregnancy Test
- Safety Laboratory (Urine/Blood)
- Blood sampling for humoral immunogenicity
- Blood sampling for cellular response
- PBMC freezing and plasma aliquots
- Blood sampling for RNA storage (only on day 0, 1, 28, 29)
- Blood sampling for troponin (only on day 28)
- Blood sampling for innate immunity (only on day 0, 1, 28 and 29)
- Training on subject diary
- Collection and review of diary

After dosing the following events will be performed **at 2 h, 4 h, 6 h, 8 h, 12 h, 24 h**:

- Vital signs (and at 0 h, before dose administration)
- Temperature (and at 0 h, before dose administration)
- (AE)/ConMed (and at 0 h, before dose administration)
- Injection site reactions & systemic events/reactions assessment

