9.4.10.3.4 Ambulatory Visits

Subjects will return to the study ward for ambulatory visits on study day 3, 7 and 14 (± 2), after the first vaccination and on study day 35, 42 (± 2), 56 (± 3), 84 (± 3) after the second vaccination. On the ambulatory visits the following events will be performed:

- Targeted Physical Examination (only on day 42)
- Vital signs/ Temperature
- 12-lead ECG (only on day 7, 14, 35, 42)
- Injection Site reaction & systemic events/ reaction assessment (only on day 3, 7, 14, 35 and 42)
- Safety Laboratory (Urine) (only on day 7, 14, 35, 42)
- Safety Laboratory (Blood) (only on day 3, 7, 14, 35, 42)
- Blood sampling for troponin (only on day 7, 14, 35, 42)
- Blood sampling for humoral immunogenicity (only on day 7, 14, 35, 42, 56, 84)
- Blood sampling for cellular response (only on day 14, 42, 56, 84)
- PBMC freezing and plasma aliquots
- Blood sampling for RNA storage (only on day 3, 7, 35)
- Blood sampling for innate immunity (only on day 3, 7, 35)
- Adverse events assessment
- Concomitant medication assessment
- Collection and review of diary

9.4.10.3.5 Ambulatory vaccination and subsequent ambulatory visits (only for subjects who gave consent to the study extension)

Subjects will return to the study ward for an ambulatory vaccination visit 12 months (± 4 months) after the first immunization.

The following interventions will be performed:

- Informed Consent
- I/E Criteria check
- Update medical history
- Weight
- Physical examination
- Vital signs / Temperature
- 12-lead ECG
- Injection Site reaction & systemic events/reaction assessment
- AE/ConMed
- Alcohol Breath Test
- Urine Drug Screen
- Urine Pregnancy Test
- Safety Laboratory (Urine/Blood)
- Blood sampling for humoral immunogenicity
- Blood sampling for cellular response
- PBMC freezing and plasma aliquots
- Blood sampling for RNA storage
- Blood sampling for troponin
- Blood sampling for innate immunity
- Dosing
- Training on subject diary

After dosing the following events will be performed **at 2 h, 4 h and 6 h**:

- Vital signs (and at 0 h, before dose administration)
- Temperature (and at 0 h, before dose administration)
- (AE)/ConMed (and at 0 h, before dose administration)
- Injection site reactions & systemic events/reactions assessment

Subjects will return to the study ward for ambulatory visits on study day 1, 3, 7 and 14 (± 2), after the third vaccination.

On the ambulatory visits the following events will be performed:

- Vital signs/ Temperature

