9.4.10.3.6 End of study/ Early termination visit

An end-of-study follow-up visit will be performed on day 180 (± 7). The following interventions will be performed:

- Physical examination
- Vital signs/Temperature
- Weight
- AE/ConMed
- Urine pregnancy test
- Safety Laboratory (Urine and Blood)
- Blood sampling for Troponin T
- Injection site reactions & systemic events/reactions assessment
- Collection subject diary
- Blood sampling for humoral immunogenicity
- Blood sampling for cellular response
- PBMC freezing and plasma aliquots

For subjects receiving 3 vaccinations, an additional end-of-study visit will be 28 (± 2 days) after the 3rd vaccination. The following interventions will be performed:

- Vital signs/Temperature
- AE/ConMed
- 12-lead ECG
- Urine pregnancy test
- Safety laboratory (urine and blood)
- Blood sampling for Troponin T
- Injection site reactions & systemic events/reactions assessment
- Collection of subject diary
- Blood sampling for humoral immunogenicity
- Blood sampling for cellular response
- PBMC freezing and plasma aliquots

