9.7.5 Clinical Laboratory Evaluations

A change in the value of a safety laboratory investigation can represent an AE if the change is clinically relevant or if, during treatment with the investigational medicinal product, a shift of a parameter is observed from a normal value to an abnormal value, or a further worsening of an already abnormal value. When evaluating such changes, the extent of deviation from the reference range, the duration until return to the reference range, either while continuing treatment or after the end of treatment with the IMP, and the range of variation of the respective parameter within its reference range, must be taken into consideration.

If, at the end of the treatment phase, there are abnormal laboratory values which were not present at baseline, further clinical or laboratory investigations should be performed until the values return to within reference range or until a plausible explanation (e.g., concomitant disease) is found for the pathological laboratory values.

The Investigator should decide, based on the above criteria and the clinical condition of a subject, whether a change in a laboratory parameter is clinically significant and therefore represents an AE.

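### Safety blood is drawn 5, 3 and 5 times in the 28 days after doses 1, 2 and 3, so by-injection tables tend to understate laboratory-detected adverse events after dose 2

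*Protocol*

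**What the plan says.** Section 8.2 makes unsolicited adverse events over the 28 days after vaccination a primary endpoint. Section 9.5.3.5.1 commits to reporting "the number of adverse events and number of subjects with adverse events by dosage level, by dosage level and injection, and the characteristics of adverse" (quote cut one word short). It names no time window for these tables and no restriction to matching time points.

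Laboratory findings can enter the tables. Section 9.7.5 allows a change to be an adverse event if it is clinically relevant or if "a shift of a parameter is observed from a normal value to an abnormal value", subject to the investigator's judgement. The holding rules in section 9.3.3.3 use the phrase "unsolicited AE (including laboratory AE and physical observations"), which places laboratory events among the unsolicited ones.

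The draws are fixed in these places:
- The Table 1a row "Safety Lab blood (Clinical Chemistry, Hematology") is ticked on days 1, 3, 7, 14 and 27, then on days 29, 35 and 42. Days 28, 56 and 84 are blank, and the next tick is day 180.
- Section 9.4.10.3.4 agrees for the outpatient visits: "Safety Laboratory (Blood) (only on day 3, 7, 14, 35, 42").
- Section 9.4.10.3.3, headed "Confinement Day -1 to Day 1 and Day 27 to Day 29", lists safety laboratory for both stays. Table 1a places the blood draws on days -1, 1, 27 and 29.
- For the boost, section 9.4.10.3.5 has "ambulatory visits on study day 1, 3, 7 and 14" and lists blood safety laboratory with no restriction by day. Section 9.4.10.3.6 adds safety blood and urine 28 (±2) days after that dose. The third-vaccination schedule table agrees.

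**The concern.** A laboratory abnormality is counted only if someone takes a sample while it is present. After dose 2 there is no visit on post-dose day 3, and no scheduled safety laboratory in post-dose days 15 to 28. Doses 1 and 3 have both a day-3 blood draw and a draw near day 28. With identical true risk after every injection, the by-injection table would be expected to show fewer laboratory events after dose 2 and a return to the higher figure after dose 3.

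There is no control arm, and each cohort has 12 subjects, so a reader will naturally look across injections within a cohort. An artefact of sampling could then be taken for a property of the vaccine.

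**Working it through.** The plan states no number of draws per injection, so there is no figure to reproduce.

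**Step 1: count scheduled samples within 28 days.** Dose 2 is given on day 28, so study days 29, 35 and 42 are post-dose days 1, 7 and 14.

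| Injection | Blood, post-dose days | n | Urine, post-dose days | n |
|---|---|---|---|---|
| 1 | 1, 3, 7, 14, 27 | 5 | 7, 14, 27 | 3 |
| 2 | 1, 7, 14 | 3 | 7, 14 | 2 |
| 3 | 1, 3, 7, 14, 28 | 5 | 7, 14, 28 | 3 |

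Three caveats apply to the count:
- The day-27 sample also serves as the check before dose 2.
- The day-28 sample after dose 3 has a window of ±2 days and may fall just outside 28 days.
- The synopsis describes safety laboratory only at screening, pre-dose and follow-up, which does not match Table 1a. The detailed schedule is used here.

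**Step 2: illustrate the effect with independent draws.** The protocol gives no risk per draw, so p is assumed to be the same after each injection and independent between draws. Then P(at least one) = 1 - (1 - p)^k for k draws. At p = 0.05:
- k = 5: 1 - 0.95^5 = 0.226
- k = 3: 1 - 0.95^3 = 0.143

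| Assumed p | 5 draws | 3 draws | 3-draw / 5-draw | Expected of 12 subjects |
|---|---|---|---|---|
| 1% | 4.9% | 3.0% | 0.61 | 0.6 vs 0.4 |
| 2% | 9.6% | 5.9% | 0.61 | 1.2 vs 0.7 |
| 5% | 22.6% | 14.3% | 0.63 | 2.7 vs 1.7 |
| 10% | 41.0% | 27.1% | 0.66 | 4.9 vs 3.3 |
| 20% | 67.2% | 48.8% | 0.73 | 8.1 vs 5.9 |

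Leaving out the day-27/28 draw gives 4 against 3 draws. At p = 0.05 that is 1 - 0.95^4 = 18.5% against 14.3%.

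**Step 3: check without independent draws.** Assume one abnormality per subject, with onset uniform over 28 days and a fixed duration. It is detected if a scheduled blood draw falls inside it.
- Duration 2 days. Doses 1 and 3: (1 + 2 + 2 + 2 + 2)/28 = 9/28 = 32%. Dose 2: (1 + 2 + 2)/28 = 5/28 = 18%.
- Duration 7 days. Doses 1 and 3: onsets in days 0 to 14 plus 7 later days, 21/28 = 75%. Dose 2: 14/28 = 50%.
- Duration 7 days with onset limited to the first 14 days: 100% after every dose.

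The loss after dose 2 therefore comes from short abnormalities around day 3 and from anything that starts after day 14.

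**The case against.** **This belongs in the analysis plan.** Section 9.8.1 defers statistical detail to a separate document that is not at hand, and table windows and splits are often settled there. That stands in part: the analysis plan may already align the time points. But the protocol itself fixes both the unequal sampling and the by-injection table, and an analysis plan can only offset the imbalance by restricting the comparison.

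**It touches a small part of safety.** This stands. A reader might infer that dose 2 is made to look safer overall. The documents do not support that:
- Solicited reactions are recorded for 14 days after every dose.
- Serious events and clinically reported events do not depend on scheduled blood.
- Both cohorts share one schedule for doses 1 and 2, so the comparison of dose levels, which is the primary objective, is balanced there.

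**The table's window is unstated.** This stands. If events were assigned to the last injection received, dose 2 could collect them from day 28 to day 180, which is 152 days against 28 for dose 1. For non-laboratory events that would push the other way. For laboratory events, dose 2 would gain only the day-180 draw and have 4 draws, still fewer than 5.

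**The size is assumed and may be smaller.** This stands. Not every shift becomes an event under section 9.7.5, successive draws are not independent, and long abnormalities that start early are caught on either schedule. Exact 95% intervals for 3/12 and 2/12 are about 5% to 57% and 2% to 48%, so the table alone could not support a claim of tolerance to dose 2 or worsening with the boost. Dose 3 is not like-for-like in any case: it is given only to consenting, eligible subjects, and cohort 1 moves to the higher dose.

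**Other outputs help.** Individual values are listed, and laboratory values and changes from baseline are summarised and graphed by dose level. These let a careful reader notice the imbalance but do not correct the by-injection counts.

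**Conclusion.** The point holds for laboratory-detected unsolicited adverse events only. The counts of 5/3/5 for blood and 3/2/3 for urine follow directly from the schedule tables and visit lists, apart from the window caveat on the last dose-3 sample. Within a common 28-day window, the by-injection comparison of these events has unequal detection and tends to understate them after dose 2.

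The size cannot be obtained from the documents. The illustration of 22.6% against 14.3%, about one subject in 12, rests on an assumed independent 5% risk per draw. Across assumed risks of 1% to 20%, the 3-draw frequency is 61% to 73% of the 5-draw frequency. The direction at equal true risk does not depend on the value chosen.

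The analysis is descriptive and no confirmatory test is planned. The consequence is a comparison that could be misread, not an inflated error rate. It is worth correcting because the table is promised and the correction is cheap.

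**What to change.** In section 9.5.3.5.1 (or in the analysis plan, if it does not already do so):
- Keep all adverse events in the main by-injection tables, and state the same 28-day window for each injection.
- Show laboratory-detected events separately from clinically reported ones.
- Add a by-injection summary of laboratory adverse events and reference-range deviations, limited to the scheduled samples that all three injections share: blood on post-dose days 1, 7 and 14, and urine on post-dose days 7 and 14. Count an abnormality if it is present at any common sample, so that one first seen on day 3 and still present on day 7 is included.
- Base any between-injection statement about laboratory events on that summary.

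The cost is a few lines of text and one extra table, with no new visits or blood. The downside is that the day-3 and day-27/28 samples do not enter that one comparison. They remain in the main tables, the time-point summaries and the listings, so no safety finding is dropped.
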